## 5.4 Safety Data Endpoints and Analyses

The safety and tolerability of ETC-1002 will be assessed by examination of TEAEs, PEs, vital signs, clinical laboratory values (serum chemistry, hematology, coagulation, and urinalysis), and weight. SP will be used for all safety analyses.

Unless otherwise stated, descriptive summaries will be performed by previous treatment group actually received in parent study and overall group.

#### 5.4.1 Adverse Events (AEs)

AEs will be coded using the Medical Dictionary for Regulatory Activities (MedDRA) Version 20.1 or later and will be categorized by system organ class (SOC) and preferred

Confidential

Page 15 of 27

Page 117 of 129

term (PT). Summary tables will focus on TEAEs; however, listings will include all AEs (with non-TEAEs flagged). An additional AE listing will be provided for AEs occurred during rollover period.

In summary tables, TEAEs will be counted as "Not Related" if relationship to study drug was recorded as 'Not Related' or "Unlikely". Events will be counted as "Related" if relationship to study drug was recorded as 'Possible', 'Probable', 'Definite' or if relationship to study drug is missing.

The severity of the AE will be characterized as mild, moderate, or severe, to the following definitions:

- Mild: Events are usually transient and do not interfere with the patient's daily activities
- Moderate: Events introduce a low level of inconvenience or concern to the patient and may interfere with daily activities
- Severe: Events interrupt the patient's usual daily activity, are incapacitating with inability to do usual activities, or significantly affect clinical status and warrant intervention and/or close follow-up

Overviews of TEAEs will include total number of TEAEs, and patient incidence of TEAEs, TESAEs, treatment-related TEAEs, treatment-related TESAEs, IMP withdrawal due to TEAEs, TEAEs with fatal outcome. Individual TEAE summary will be presented by previous treatment group in parent study and overall containing the following counts and percentages for:

- patients with TEAEs by SOC and PT
- patients with TEAEs by PT
- patients with TEAEs by SOC, PT, and maximum severity
- patients with treatment-related TEAEs
- patients with treatment-related TEAEs by PT
- patients with treatment-related TEAEs by SOC and PT
- patients with treatment-emergent serious adverse events (TESAEs) by SOC and PT
- patients with TESAEs by PT
- patients with TESAEs by SOC, PT, and maximum severity
- patients with treatment-related TESAEs
- patients with treatment-related TESAEs by SOC and PT
- TEAEs leading to withdrawal of IMP by SOC and PT
- fatal TEAEs by SOC and PT

Preferred terms for TEAEs that occurred in more than 1% of subjects overall will be plotted using the overall group. This plot will be repeated for TESAEs in the overall group.

#### Confidential

Page 16 of 27

In addition, summary tables will be provided, by prior treatment group and overall, for the number and percent of patients experiencing:

- adjudicated major adverse cardiovascular events and mortality (MACE) by event type
- non-CV deaths (non-MACE),
- nonfatal myocardial infarction [MI] (MACE),
- nonfatal stroke (MACE),
- hospitalization for unstable angina (MACE),
- coronary revascularization (MACE),
- noncoronary arterial revascularization (non-MACE),
- hospitalization for heart failure (non-MACE) using standardized definitions.

The TEAE, treatment-related TEAE, TESAE, and AESI summaries by SOC, PT and maximum severity will be provided for relevant subgroups described in 5.2.5 with the exception of baseline LDL category.

The AE overview summaries will count a patient at most once in each AE category (at the "highest/most extreme" designation of each category regardless of preferred term) and percentages will be based on the total number of patients in the safety population.

In addition to a comprehensive listing of all AEs (with non-TEAEs flagged), separate listings will be generated for serious adverse events, TEAEs resulting in withdrawal of study drug, and TEAEs with a fatal outcome, investigator reported major adverse cardiovascular events and mortality, and adjudicated major adverse cardiovascular events and mortality.

#### 5.4.2 Adverse Events of Special Interest

Adverse events of special interest (AESI) will be identified based on a pre-defined list of preferred terms provided by the sponsor (Appendix 2).

AESI will be presented in a listing and summarized by SOC, PT, and previous treatment group in parent study and overall in OLE study. A separate table for treatment-emergent AESI resulting in the discontinuation of study drug will be summarized by SOC, PT, and previous treatment group in the parent study and overall in OLE study.

In addition to adverse events, AESI is also being evaluated based on safety lab parameters. The details are provided in 5.4.5.

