11. ADVERSE AND SERIOUS ADVERSE EVENTS

11.1. Adverse Events

11.1.1. Definition of Adverse Events

An AE is defined as any untoward medical occurrence in a clinical investigation patient administered a pharmaceutical product, including control, and which does not necessarily have a causal relationship with treatment. The investigator is responsible for ensuring that any adverse events observed by the investigator or reported by the patient are recorded in the patient's medical record.

An AE can be:

- Any unfavorable and unintended sign/symptom, including an abnormal laboratory finding, or disease temporally associated with the use of a medicinal product, whether or not considered related to the medicinal product
- Any new disease or exacerbation of an existing disease
- Laboratory abnormality or diagnostic test abnormalities (eg, electrocardiogram [ECG] or X-ray) should be reported as an AE if one of the following occurs
 - Treatment required due to the abnormality
 - Discontinuation of IMP
 - Per Investigator judgement

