11.1.3. Reporting for Adverse Events

All AEs occurring during the course of the study (starting from signing informed consent through 30 days after last dose of bempedoic acid) will be collected on the AE eCRF. Patients should be instructed to report any AE that they experience to the investigator. Investigators should make an assessment for AEs at each visit and record the event on the appropriate AE eCRF.

Wherever possible, a specific disease or syndrome rather than individual associated signs and symptoms should be identified by the investigator and recorded on the eCRF. A cluster of signs and symptoms that results from a single cause should be reported as a single AE (eg, fever,

Bempedoic Acid Clinical Study Protocol 1002-050

elevated white blood cells [WBC], cough, abnormal chest X-ray, etc, can all be reported as "pneumonia" if that is the final diagnosis). However, if an observed or reported sign or symptom is not considered a component of a specific disease or syndrome by the investigator, it should be recorded as a separate AE on the eCRF. Additionally, the condition that led to a medical or surgical procedure should be recorded as the AE, not the procedure itself.

Any medical condition already present at screening or baseline should not be reported as an AE unless the medical condition or signs or symptoms present at baseline worsens in severity or seriousness at any time during the study. In this case, it should be reported as an AE.

Clinically significant abnormal laboratory or other examination findings that are detected during the study or are present at baseline and significantly worsen during the study should be reported as AEs. The investigator will exercise his or her medical and scientific judgment in deciding whether an abnormal laboratory finding or other abnormal assessment is clinically significant. Significant abnormal laboratory values occurring during the clinical study will be followed until repeat tests return to normal, stabilize, or are no longer clinically significant. Any abnormal test that is determined to be an error does not require reporting as an AE.

Each AE is to be evaluated for duration, severity, seriousness, and causal relationship to the IMP. For each AE, the following information will be recorded:

- Description of the event (eg, headache)
- Date of onset
- Date of resolution (or that the event is continuing)
- Action taken as a result of the event
- Seriousness of the event
- Severity of the event

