# 8.2 Appendix 2: Adverse Event of Special Interest (AESI)

Adverse Event Terms per Protocol	Associated MedDRA Preferred Terms
Creatine kinase elevations	Blood creatine phosphokinase abnormal
Creatine kinase elevations	Blood creatine phosphokinase increased
Creatine kinase elevations	Blood creatine phosphokinase MM abnormal
Creatine kinase elevations	Blood creatine phosphokinase MM increased
New onset or worsening diabetes mellitus	Blood glucose abnormal
New onset or worsening diabetes mellitus	Blood glucose increased
New onset or worsening diabetes mellitus	Diabetes mellitus
New onset or worsening diabetes mellitus	Diabetes mellitus inadequate control
New onset or worsening diabetes mellitus	Diabetic ketoacidosis
New onset or worsening diabetes mellitus	Glucose tolerance impaired
New onset or worsening diabetes mellitus	Glucose urine present
New onset or worsening diabetes mellitus	Glycosuria
New onset or worsening diabetes mellitus	Glycosylated haemoglobin increased
New onset or worsening diabetes mellitus	Hyperglycaemia
New onset or worsening diabetes mellitus	Impaired fasting glucose
New onset or worsening diabetes mellitus	Ketoacidosis
New onset or worsening diabetes mellitus	Ketosuria
New onset or worsening diabetes mellitus	Ketosis
New onset or worsening diabetes mellitus	Type 2 diabetes mellitus
New onset or worsening diabetes mellitus	Urine ketone body present
Hepatic disorders	Alanine aminotransferase abnormal
Hepatic disorders	Alanine aminotransferase increased
Hepatic disorders	Aspartate aminotransferase abnormal
Hepatic disorders	Aspartate aminotransferase increased
Hepatic disorders	Blood bilirubin abnormal
Hepatic disorders	Blood bilirubin increased
Hepatic disorders	Hepatic enzyme abnormal
Hepatic disorders	Hepatic enzyme increased
Hepatic disorders	Hypertransaminaseaemia
Hepatic disorders	Liver function test abnormal
Hepatic disorders	Liver function test increased
Hepatic disorders	Transaminases abnormal
Hepatic disorders	Transaminases increased
Hypoglycemia	Blood glucose abnormal
Hypoglycemia	Blood glucose decreased
Hypoglycemia	Hypoglycaemia
Hypoglycemia	Hypoglycaemic coma
Hypoglycemia	Hypoglycaemic encephalopathy
Hypoglycemia	Hypoglycaemic seizure
Hypoglycemia	Shock hypoglycaemic
Metabolic acidosis	Metabolic acidosis
Muscular disorders	Muscular weakness
Muscular disorders	Muscle necrosis
Confidential	Page 26 of 27

Confidential

Page 26 of 27

Muscular disorders	Muscle spasms
Muscular disorders	Myalgia

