Muscular disorders	Myoglobin blood increased
Muscular disorders	Myoglobin blood present
Muscular disorders	Myoglobin urine present
Muscular disorders	Myoglobinaemia
Muscular disorders	Myoglininuria
Muscular disorders	Myopathy
Muscular disorders	Myopathy toxic
Muscular disorders	Necrotizing myositis
Muscular disorders	Pain in extremity
Muscular disorders	Rhabdomyolysis
Neurocognitive/Neurologic disorders	Amnesia
Neurocognitive/Neurologic disorders	Cognitive disorder
Neurocognitive/Neurologic disorders	Confusional state
Neurocognitive/Neurologic disorders	Disorientation
Neurocognitive/Neurologic disorders	Memory impairment
Neurocognitive/Neurologic disorders	Mental status changes
Renal disorders	Acute kidney injury
Renal disorders	Acute prerenal failure
Renal disorders	Blood creatinine abnormal
Renal disorders	Blood creatinine increased
Renal disorders	Blood urea abnormal
Renal disorders	Blood urea increased
Renal disorders	Blood urea nitrogen/Creatinine ratio increased
Renal disorders	Creatinine renal clearance abnormal
Renal disorders	Creatinine renal clearance decreased
Renal disorders	Glomerular filtration rate abnormal
Renal disorders	Glomerular filtration rate decreased
Renal disorders	Gout
Renal disorders	Oliguria
Renal disorders	Prerenal failure
Renal disorders	Renal failure
Renal disorders	Renal function test abnormal
Renal disorders	Renal impairment

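### In the LFT and CK table, a lone last abnormal value counts as both 'single' and 'repeated and confirmed'; secondarily, the hepatic AESI list holds laboratory terms only

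*SAP*

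**What the plan says.** **Laboratory table (SAP v1.3, 5.4.4.1 Hepatic Safety; same text in v1.2, 5.4.5.1).** Patients are counted for ALT and AST above 3 and 5 times ULN, CK above 5 and 10 times ULN, and ALT and/or AST combined. A *single incident* means only one abnormal incident. *Repeated and confirmed* is met by any one of several criteria. The first is that the last on-study value is abnormal. The next refers to the last on-treatment value. The final one is an abnormal value followed by another for the same test. The text between the second and third criteria runs together, perhaps from PDF extraction. CK stands in the same sentence and is handled by the same rule.

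**AESI selection (SAP v1.3, 5.4.2 and Appendix 2).** On the adverse event side, "Adverse events of special interest (AESI) will be identified based on a pre-defined list of preferred terms provided by the sponsor (Appendix 2". The hepatic rows are abnormal/increased pairs for ALT, AST, bilirubin, hepatic enzyme, liver function test and transaminases, plus "Hypertransaminaseaemia". The creatine kinase rows, such as "Blood creatine phosphokinase increased", are also all laboratory terms. The renal rows include diagnoses such as "Acute kidney injury". Section 5.4.2 adds that AESI are also evaluated on laboratory parameters, and 5.4.4 lists ALT/AST, bilirubin and potential Hy's law cases for that purpose.

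**Recording rules (protocol 11.1.1 and 11.1.3).** Section 11.1.3 asks that, where possible, "a specific disease or syndrome rather than individual associated signs and symptoms should be identified by the investigator", and says that "A cluster of signs and symptoms that results from a single cause should be reported as a single AE". Section 11.1.1 says a laboratory abnormality "should be reported as an AE if one of the following occurs", and one of the listed conditions is "Discontinuation of IMP". A later sentence of 11.1.3 also asks for clinically significant laboratory findings to be reported.

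**The concern.** The two labels in the laboratory table read as alternatives, and a reader will take *repeated and confirmed* to mean that a second abnormal value exists. Under the definitions it need not. A lone value can be labelled confirmed, and the same patient can be counted in both rows. Week 82 is an off-drug visit, so that lone value may not even be an on-treatment finding. What is at stake is how a reader interprets the liver and CK tables in a study whose primary objective is long-term safety.

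The secondary concern is completeness. A liver event entered only as a diagnosis matches none of the hepatic terms. The hepatic AESI count would then be short by that event, and nothing in the table would say so.

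**Working it through.** The plan states no figure for either point, so there is none to reproduce. The checks are counts and logic, not rates.

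**1. Overlap of the two definitions.** Inputs: scheduled post-baseline laboratory visits at Weeks 12, 52, 78 and 82 (SAP 3.2.5, Appendix 1); a patient treated to Week 78, so Week 78 is the last on-treatment value and Week 82 the last on-study value; 'abnormal' means above the table's threshold. There are four ways to have exactly one abnormal value:

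| Only abnormal value | Single | Last on-study abnormal | Last on-treatment abnormal | Both categories? |
|---|---|---|---|---|
| Week 12 | yes | no | no | no |
| Week 52 | yes | no | no | no |
| Week 78 | yes | no | yes | only if the on-treatment words are a separate criterion |
| Week 82 | yes | yes | no | yes |

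So 1 of 4 patterns overlaps on the intact first criterion alone, and 2 of 4 if the on-treatment words count separately.

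The reverse can also occur. Suppose 'followed by' means the next value, and a patient is abnormal at Week 12, normal on a repeat, abnormal at Week 52, and normal at Weeks 78 and 82. That patient is neither single nor repeated and confirmed. If 'followed by' means any later value, the patient is repeated and confirmed. The text does not settle which applies.

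**2. Does a four-row replacement work?** Rows, assigned in order: (a) an abnormal value whose next value is also abnormal; (b) otherwise, last on-study value abnormal; (c) otherwise, last on-treatment value abnormal with a later off-treatment value not abnormal; (d) all other patients with an abnormal value.

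- Four visits: 2^4 − 1 = 15 patterns have at least one abnormal value. Row (a) holds 8, (b) 3, (c) 2 and (d) 2; 8 + 3 + 2 + 2 = 15. The SAP's *repeated and confirmed* set, under the next-value reading with the on-treatment criterion included, is (a) + (b) + (c) = 13.
- Six draws (two unscheduled repeats added, draw 5 the last on-treatment value, draw 6 Week 82): 2^6 − 1 = 63 patterns. Row (a) holds 43, (b) 8, (c) 5 and (d) 7; 43 + 8 + 5 + 7 = 63. The SAP set is 43 + 8 + 5 = 56. Without row (c), rows (a) and (b) give only 51, and the 5 patterns with an on-drug elevation that is normal off drug drop out of sight.

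**3. Appendix 2 term counts.**

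| List | Terms | Laboratory | Clinical |
|---|---|---|---|
| Hepatic | 13 | 13 | 0 |
| Creatine kinase | 4 | 4 | 0 |
| Muscular | 14 | 5 | 9 |
| Renal | 17 | 10 | 7 |

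The CK list has the muscular list beside it (together 9 clinical of 18). The hepatic list has no clinical counterpart.

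**4. Which outputs are affected.** A diagnosis-only liver event would be absent from the AESI listing, the AESI summary and the AESI tables for up to 8 subgroup variables (9 in 5.2.5, less baseline LDL). It could also be absent from the table of AESI leading to discontinuation. This last is less likely: where abnormal liver tests led to stopping IMP, protocol 11.1.1 calls for a laboratory AE, which would match the list. The event would remain in the TEAE, SAE, withdrawal and fatal tables as applicable and in the full AE listing. It would also appear in the laboratory AESI summaries if a study sample was taken and exceeded a threshold. Safety samples are not scheduled between Weeks 12 and 52, so that last safeguard is partial.

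**The case against.** On the laboratory table, it can be said that treating a last abnormal value as confirmed is a cautious choice, because nothing later shows it resolved. The protocol also requires repeat tests after a raised ALT, AST or CK (10.1.4.3.1 and 10.1.4.3.3), and unscheduled values are taken into account (5.4.4). Both points stand. Caution justifies keeping such patients visible, and repeats make an unrepeated last value less common. Neither justifies calling a value confirmed when no second one exists, and neither removes the double count. Nor does the overlap rest on the run-together text, since the first criterion is intact.

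On the hepatic list, the laboratory focus may be deliberate. Protocol 11.3 describes hepatic monitoring through the safety laboratories, the superseded SAP v1.0 assessed hepatic safety through enzymes and bilirubin, and no document requires every AESI list to mix laboratory and clinical terms. This largely stands. The contrast with the renal and muscular lists shows a gap, not an error.

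A reader might infer from the 0 of 13 count that liver injuries would go unreported, or that the SAP contradicts the protocol. The documents support neither. The general adverse event outputs still carry the event, and the protocol's recording rules pull both ways, so a diagnosis-only record is possible but not the expected path in every case.

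**Conclusion.** The overlap in 5.4.4.1 is a definite drafting fault: 1 of the 4 one-abnormal-value patterns falls in both categories, or 2 of 4 if the on-treatment words are a separate criterion. This assumes that an incident is one value above the threshold and that the patient is treated to Week 78 with values at the four scheduled visits. These are patterns, not proportions of patients. The hepatic term list is a smaller matter, best treated as an optional supplement. No rate can be derived from the documents for either point. The primary endpoint, patient incidence of TEAEs, is unaffected, and the study is descriptive with no planned inference. Severity is minor.

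**What to change.** **Section 5.4.4.1.** For each test and threshold, on post-baseline values including unscheduled repeats, replace the two categories with exclusive rows assigned in this order:

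- (a) confirmed: an abnormal value whose next value of the same test is also above the threshold;
- (b) unconfirmed, last on-study value above the threshold;
- (c) unconfirmed, last on-treatment value above the threshold, with a later off-treatment value not above it;
- (d) all other patients with an abnormal value.

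For the combined ALT and/or AST line, assign each patient once in the same order. Apply the same rows to CK. Under the next-value reading, rows (a) to (c) together recover the present *repeated and confirmed* set, so the cautious handling of last values stays visible.

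**Appendix 2.** Add a supplementary hepatic AESI count that includes clinical hepatic diagnoses, with its terms written down before the rerun. Show it beside the existing 13-term count and label it as added after the interim analyses.

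**Cost.** One definition, one appendix entry and a rerun of existing tables, with no new data. The supplementary hepatic count may be slightly higher than the 13-term count. The definitions and the hepatic list were already in v1.2, and the Day 120 addendum lists an abnormal liver function summary (Table 14.3.6.4), so a footnote on comparability with the interim outputs is needed.

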11.3. Adverse Events of Special Interest

Adverse events of special interest (AESI) are included in this protocol for reasons either associated with other lipid lowering therapies or where deemed important based on nonclinical data. AESI for this protocol include: metabolic acidosis (clinical laboratories), hypoglycemia, muscular (AE and CK evaluation), hepatic, and neurocognitive/neurologic events.

Muscle: Muscle events have been associated with statins (Thompson 2003) and other lipidlowering therapies and are mentioned in the product information for these therapies. Muscle symptoms through AE review, CK elevations, and symptoms of potential myopathy will be closely monitored.

Hepatic: Hepatic function will be monitored throughout with the clinical safety labs. More detailed investigation will occur if the safety clinical laboratory results are $>3 \times$ ULN.

Neurocognitive Events: Theoretically, it is possible that lipid-lowering agents that disrupt cholesterol homeostasis in the brain could impact neurological function, and there have been reports of cognitive impairment (eg, memory loss) associated with the use of statin drugs

(FDA 2012). Summarization of events will occur using prespecified Medical Dictionary for Regulatory Activities (MedDRA) terms outlined in the statistical analysis plan (SAP).

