12.6. Other Safety Endpoints

Laboratory Results

Actual value or change from baseline (where appropriate) in clinical safety laboratories, including hematology, blood chemistry, HbA_{1C}, glucose, and urinalysis will be summarized at each scheduled visit.

Shift tables for selected safety laboratory parameters will be provided.

Physical Measurements

Height and weight will be summarized at each scheduled visit.

Vital Signs

Hear rate, SBP and DBP will be summarized at each scheduled visit.

Hepatic Safety

Actual value and change from baseline in liver-associated enzymes and TB will be summarized at each visit. In addition, the number and percent of patients with normal vs. abnormal values for ALT, AST, and TB will be summarized by their baseline and postbaseline status. Hy's law criteria (>3 × ULN for either ALT or AST, with accompanying TB >2 × ULN or patient's baseline) will also be applied to the data; any potential Hy's law cases will be listed separately. In the case of patients with Gilbert's disease, TB will be fractionated and the determination of $2 \times ULN$ based upon direct (conjugated) bilirubin. For patients with Gilbert's Disease $2 \times$ the conjugated bilirubin will be used as the criterion.

Musculoskeletal Safety

Adverse events of muscle-related symptoms will be summarized. Creatine kinase levels will be summarized by the value and change from baseline in the value, by visit. In addition, the number and percent of patients with normal vs. abnormal CK values will be summarized by their baseline and post-baseline status.

Diabetes and Hyperglycemia

Cases of new onset of diabetes will be recorded as AEs and will be summarized using the appropriate SOC. These events will be summarized by severity and relationship to study drug. Glucose and HbA_{1C} will be monitored at baseline and at Weeks 12, 52 and 78, and be summarized by history of diabetes.

Renal Safety

Baseline eGFR will be summarized for actual value and for baseline eGFR categories. Shift tables of eGFR category from baseline over the study, will be provided. Shift tables of urine protein (negative/positive) from baseline over the study, will be provided. Values of CK will be summarized by baseline eGFR category.

Neurocognitive Events

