Table 14.3.3.4.1	and Maximum Severity	
	Exposure-Adjusted Incidence of Treatment-	Safety
	emergent Adverse Events of Special Interest	3
	(AESIs) by System Organ Class, Preferred Term	Population - by Gender
Table 14.3.3.4.2	and Maximum Severity	Gender
	Exposure-Adjusted Incidence of Treatment-	Safety
	emergent Adverse Events of Special Interest	Population - by
Table 14.3.3.4.3	(AESIs) by System Organ Class, Preferred Term	Age

Confidential

Page 13 of 23

	and Maximum Severity	
Table 14.3.3.4.4	Exposure-Adjusted Incidence of Treatment- emergent Adverse Events of Special Interest (AESIs) by System Organ Class, Preferred Term and Maximum Severity	Safety Population – by Baseline CVD risk Category
Table 14.3.3.4.5	Exposure-Adjusted Incidence of Treatment- emergent Adverse Events of Special Interest (AESIs) by System Organ Class, Preferred Term and Maximum Severity	Safety Population – by Baseline Statin Intensity
Table 14.3.3.4.6	Exposure-Adjusted Incidence of Treatment- emergent Adverse Events of Special Interest (AESIs) by System Organ Class, Preferred Term and Maximum Severity	Safety Population – by Race
Table 14.3.3.4.7	Exposure-Adjusted Incidence of Treatment- emergent Adverse Events of Special Interest (AESIs) by System Organ Class, Preferred Term and Maximum Severity	Safety Population – by History of Diabetes
Table 14.3.3.4.8	Exposure-Adjusted Incidence of Treatment- emergent Adverse Events of Special Interest (AESIs) by System Organ Class, Preferred Term and Maximum Severity	Safety Population – by Baseline Body Mass Index (BMI) Group
Table 14.3.3.4.9	Exposure-Adjusted Incidence of Treatment- emergent Adverse Events of Special Interest (AESIs) by System Organ Class, Preferred Term and Maximum Severity	Safety Population – by Region
Table 14.3.3.5.1	Exposure-Adjusted Incidence of Related Treatment-emergent Adverse Events by System Organ Class and Preferred Term	Safety Population

Confidential

Page 14 of 23

Exposure-Adjusted Incidence of Related	Safety
	Population - by
	Gender
	Safety
	3
	Population - by
Organ Class and Preferred Term	Age
	Safety
Exposure-Adjusted Incidence of Related	Population –
Treatment-emergent Adverse Events by System	by Baseline
Organ Class and Preferred Term	CVD risk
	Category
Exposure Adjusted Incidence of Deleted	Safety
	Population –
	by Baseline
Organ Class and Preferred Term	Statin Intensity
Exposure-Adjusted Incidence of Related	Safety
	Population –
	by Race
	Safety
Exposure-Adjusted Incidence of Related	Population –

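### The AESI tables in SAP v1.3 are laid out by SOC and preferred term, so six of the eight Appendix 2 categories have no specified count of patients with at least one event

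*SAP*

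**What the plan says.** Protocol 11.3 defines the events of special interest by clinical group: "AESI for this protocol include: metabolic acidosis (clinical laboratories), hypoglycemia, muscular (AE and CK evaluation), hepatic, and neurocognitive/neurologic events". Protocol 12.4 then asks for AESIs to be tabulated by SOC and preferred term (PT), along with the other adverse event tables.

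SAP v1.3 follows that layout throughout:

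- **Main table (5.4.2):** "AESI will be presented in a listing and summarized by SOC, PT, and previous treatment group in parent study and overall in OLE study".
- **Discontinuation table (5.4.2):** "A separate table for treatment-emergent AESI resulting in the discontinuation of study drug will be summarized by SOC, PT", again by prior treatment and overall.
- **Subgroup tables (5.4.1):** "The TEAE, treatment-related TEAE, TESAE, and AESI summaries by SOC, PT and maximum severity will be provided for relevant subgroups", leaving out only the baseline LDL subgroup.
- **Day 120 addendum:** the main AESI table and its subgroup versions are titled "Adverse Events of Special Interest (AESIs) by System Organ Class, Preferred Term and Maximum Severity".

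AESIs are identified from the PT list in Appendix 2. That list has two columns. The one headed "Adverse Event Terms per Protocol" holds a clinical category, and the other holds the PT. The category column does not appear in the description of any AESI table.

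**The concern.** Safety is the primary objective of this study, and the AESIs are the safety questions fixed in advance. A reader of the study report will first want to know how many patients had any hepatic event, any muscular event or any renal event, and how that differs by prior treatment. A table by SOC and PT does not answer this where a category holds several terms. One patient can have more than one of them, so PT counts cannot be added up to a number of patients.

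If the category counts are not specified, they will either be missing or be produced after the data are seen, without a stated counting rule.

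**Working it through.** **1. Categories in Appendix 2 (SAP v1.3), counted by row**

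| Category | PT rows |
|---|---|
| Creatine kinase elevations | 4 |
| New onset or worsening diabetes | 16 |
| Hepatic | 13 |
| Hypoglycemia | 7 |
| Metabolic acidosis | 1 |
| Muscular | 14 |
| Neurocognitive/neurologic | 6 |
| Renal | 17 |

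The total is 4 + 16 + 13 + 7 + 1 + 14 + 6 + 17 = 78 rows. Blood glucose abnormal is listed under both diabetes and hypoglycemia, so there are 77 distinct PTs.

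**2. Which categories lack a count**

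- Metabolic acidosis is one PT, so its PT row is exactly the category incidence.
- Neurocognitive events have their own summary in 5.4.2.1.
- That leaves 8 − 2 = 6 categories (CK, diabetes, hepatic, hypoglycemia, muscular, renal), each with 4 to 17 PTs and no adverse event summary of its own in SAP v1.3.

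**3. Whether another rule supplies the count**

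Section 5.4.1 counts each patient at most once per category, but it states this for the overview summaries. The overview items are TEAEs, serious TEAEs, related TEAEs, related serious TEAEs, withdrawals of study drug and fatal events. AESIs are not among them.

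**4. What PT rows can tell the reader**

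Let n₁, …, n_k be the patient counts for the PTs of one category, C the patients with at least one of them, and N the number treated. Then

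max(n₁, …, n_k) ≤ C ≤ min(N, n₁ + … + n_k).

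The plan has no figure of its own to reproduce here. The protocol expects about 1300 patients. The PT counts below are assumed, for illustration only.

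- Two hepatic terms, 13 patients each: lower bound 13/1300 = 1.0%, upper bound (13 + 13)/1300 = 2.0%.
- Two hepatic terms, 20 and 16 patients: 20/1300 = 1.5% to 36/1300 = 2.8%.
- Three muscular terms, 40, 35 and 30 patients: 40/1300 = 3.1% to 105/1300 = 8.1%.

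A row that counts each patient once would replace each range with one number.

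**5. Protocol 12.6 beside SAP v1.3**

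Protocol 12.6 states, under musculoskeletal safety, "Adverse events of muscle-related symptoms will be summarized". It also promises a summary of new-onset diabetes events by severity and relationship. The matching SAP sections cover CK only (5.4.4.2) and glucose and HbA1c only (5.4.4.3). Category rows would help to deliver both.

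**The case against.** The best defence is that SAP v1.3 does what protocol 12.4 asks. The study is descriptive, the primary endpoint (patient incidence of TEAEs) is untouched, and the AESI listing together with Appendix 2 keeps everything needed to derive category counts. All of that is true. It makes this a matter of better presentation, with no data lost. It does not supply the counts or a rule for making them.

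The second defence is the laboratory side of the AESI evaluation. Section 5.4.4 summarises abnormalities in liver tests, CK, glucose, HbA1c, creatinine and eGFR. Section 5.4.4.1 includes a count of patients with ALT and/or AST above 3 and 5 times the ULN, which settles the overlap between those two tests at those thresholds. For the hepatic category, where every Appendix 2 term is a laboratory-type term, this softens the point. But threshold crossings and reported events are different things. Under protocol 11.1.1 a laboratory abnormality becomes an adverse event through treatment, discontinuation of study drug or investigator judgement. SAP 5.4.2 itself presents the laboratory evaluation as additional to the adverse events. Myalgia, muscle spasms and pain in extremity have no laboratory counterpart at all.

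Three stronger readings are tempting, and the documents do not support them:

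- **That no AESI table gives the incidence of any event of interest.** Metabolic acidosis is exact from its single row, and neurocognitive events have a separate summary.
- **That the SAP departs from the protocol.** Protocol 12.4 prescribes the same layout.
- **That particular SOC rows mix several categories, or that one category is split over several SOCs.** This needs the MedDRA SOC of each term, which neither document gives. For the same reason one cannot rule out that some SOC subtotal happens to match a category. The plan does not ensure it.

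**Conclusion.** The point holds as an inexpensive improvement. For six of the eight Appendix 2 categories, SAP v1.3 specifies no adverse-event-based count of patients with at least one event: not overall, not by prior treatment, not for discontinuation of study drug and not in subgroups.

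The size depends on how far the terms overlap within patients, which cannot be known in advance. With two terms the upper bound is at most twice the lower, as in the 1.0% to 2.0% example. With more terms it can be a larger multiple, as in the three-term example of 3.1% to 8.1%. These percentages rest on assumed PT counts and on the expected 1300 patients. The row count and the absence of category rows rest on the text alone.

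**What to change.** In SAP 5.4.2 and 5.4.1:

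- Add one row per Appendix 2 category to the AESI tables (main, discontinuation, maximum severity, subgroups). Each row gives the number and percent of patients with at least one treatment-emergent event in that category, counted once per category, by prior treatment and overall.
- Place the PTs beneath each category row, and keep the SOC and PT layout as a secondary presentation. This stays consistent with protocol 12.4.
- State how Blood glucose abnormal is counted, since it sits under both diabetes and hypoglycemia.
- While editing 5.4.2, correct its pointer for the laboratory details. It names 5.4.5, which in v1.3 is the physical examination; the laboratory section is 5.4.4.

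The cost is a few extra table rows, one counting rule and a grouping variable that Appendix 2 already supplies. No new data are needed.
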